## 7.0 Evaluation During Treatment

### 7.1 Clinical Evaluation

Patients will be evaluated every 2 weeks (+/- 2 days) through week 4, then every 4 weeks (+/- 1 week) during the vaccination/treatment. For subjects in the adjuvant cohort, this schedule will continue through week 8, for patients in the metastatic cohort, this will continue until Resiquimod treatment is discontinued. With each patient visit, the evaluation will consist of complete interim history and physical examination, including measurement of vital signs, performance status, and weight. Patients will be evaluated for toxicity and concomitant medications at each visit. Toxicities will be recorded on the toxicity sheet and the medications will be recorded in the patient's electronic medical record. Patients will have a complete blood count (CBC), with differential, PT/PTT, serum electrolytes, BUN, creatinine, glucose, albumin, alkaline phosphatase, ALT, AST, LDH, calcium, and total bilirubin tested at baseline and then tested approximately every 2-4 weeks (using pediatric blood collection tubes if feasible).

For patients in the adjuvant arm,

CT scans of the chest, abdomen, and pelvis will be done at baseline, week 8, (+/- 1 week) and then repeated at 8 week (+/- 1 week) intervals during resiquimod treatment. MRI/CT of the brain will be done at baseline and repeated at the time of the CT scans if clinically indicated.

At discontinuance of vaccination in the adjuvant cohort or resiquimod treatment in the metastatic cohort, clinical follow-up, labs, and staging studies (CT, MRI, PET scans) will be obtained at the discretion of the treating physician following standard clinical pathways.

Subjects in either cohort will be followed on study for 12 months after the completion of therapy (vaccination in the adjuvant cohort, Resiquimod in the metastatic cohort) unless they meet criteria for withdrawal as per section 10.0. Clinical events will be tracked from the physician determined routine clinical follow-up during this period. Clinical events that occur after this period on study may be retroactively recorded from the patient's medical record including tumor progression and death.

### 7.2 Immunological Evaluations

Sixty mL (4 tablespoons) of peripheral blood will be obtained at weeks 0, 2, 4, 8, 12, 16, 20, and 24 (+/- 1 week). Weeks 0, 8 and 16 will collect only ten mL (2/3 tablespoon) of peripheral blood by phlebotomy in addition to the leukopheresis. If the leukopheresis is not performed for those time points, then we will collect Sixty mL (4 tablespoons) of peripheral blood. When feasible, biopsies of the vaccine site will be obtained and tumor will be obtained as outlined in section 7.3.

**7.2.1** Flow cytometric analysis

Flow cytometry will be utilized to determine the percentage of antigen specific CD8+ (gp100(g209-2M) or CD4+ (MAGE -3) T-cells and the percentage of cells expressing phenotypic markers to assess activation status of T-cells in the circulation and at the tumor site. In addition, this technique will be used to determine the nature of the inflammatory infiltrate at the tumor site in the presence or absence of TLR agonist.

**7.2.2** Immunohistochemistry (IHC)

IHC will be performed on vaccine site and tumor biopsies and will be used to assess the nature of the inflammatory infiltrate at these sites in the presence or absence of TLR agonists. Specifically, antibodies specific for pDCs, mDCs, NK cells, and T-cells will be used.

**7.2.3** ELISPOT/ Luminex

These assays will be utilized to determine specific cytokine release or number of antigen specific spots per 10^4 CD8+ (for gp100(g209-2M) or CD4+ (for MAGE-3) T-cells. In addition, Luminex assays will be utilized to determine the cytokine profile of antigen-specific T-cells.

**7.2.4** Quantitative RT-PCR

This technique will be used to determine the gene expression of specific cytokines at the vaccine and tumor sites.

**7.2.5** Leukapheresis will be utilized for blood collection together with a ten mL phlebotomy to obtain peripheral lymphocytes and plasma at three time points when feasible. Leukapheresis will be performed prior to treatment, after treatment at week 8 (+/- 1 week), and at week 16 (+/- 1 week). This is for both cohorts. Each leukapheresis will consist of a 7.5 to 10 liter exchange lasting about three hours.

**7.2.6** Plasma collected from phlebotomy will be used to measure reactivity of patient's antibodies against tumor antigens.

**7.3** Biopsies: Two areas will be biopsied during the course of this study, the vaccine site and the tumor.

**Vaccine biopsies:** Vaccine sites will be biopsied from all patients in the study when feasible. The vaccine site biopsied will be a GP100 vaccine site. The vaccine site will be identified and a punch biopsy taken of full thickness skin with standard sterile technique and closure. Vaccine sites will be biopsied at 24 hrs (+/- 6 hours) after the first gp100(g209-2M) vaccine and at week two of vaccination. These biopsies will occur the day following the vaccination for that week. Failure to obtain vaccine biopsies due to refusal, discretion of the investigators or infeasibility will not constitute a violation of the trial.

**Tumor biopsies** will be taken from patients in the cohort with metastatic disease. There will be no tumor biopsies in patients enrolled in the adjuvant cohort. The first

biopsy will be taken as a base line at any time after enrollment onto the trial, but prior to the first vaccination. A second tumor biopsy will be taken at week 8 prior to the first dose of R848 on the tumors, and at week 12 (4 weeks after initiating R848 therapy on the tumors, but at any time during that week) Tumors will be randomly selected when biopsied, but when feasible, a biopsy will be taken of both a treated lesion and untreated lesion at week 12. Tumor biopsies may be taken using any biopsy method to optimize tumor yield using standard sterile techniques. Tumor volume may not allow for all biopsies to be obtained in all individuals, in this case pre-vaccine biopsies and week 12 will take precedence. Tumor biopsies are at the option of the enrolled subject and the investigators, and failure to obtain tumor biopsies due to refusal, inadequate remaining tumor volume, discretion of the investigators or infeasibility will not constitute a violation of the trial.

#### 7.4 Samples for Research

Leftover blood, tissue, and T-cells (and possibly genetic material extracted from these samples) will be stored for research. These samples may be analyzed by MD Anderson and other qualified investigators. These samples will be de-identified. The research studies involving these samples will be performed following IRB approved protocols. The samples used in these research studies will be to gain further information about the disease and will not be used for future treatment decisions.

### 8.0 Serious Adverse Event Reporting (SAE)

Vaccines are usually well-tolerated. They may cause discomfort, swelling, and/or redness around the injection site. While there has not been significant autoimmune symptoms caused by gp100(g209-2M) or MAGE-3 peptide vaccines alone, patients who experience any Grade III or greater autoimmune reactivity, except for local skin reactions, will be taken off the study. The occurrence of 3 patients with Grade III or greater toxicity will stop the entry of the study until an assessment of the risks, coordination with MD Anderson IRB and appropriate modifications of the informed consent can be completed.

The most frequent systemic toxicities associated with Resiquimod are fever, fatigue, headache, pain, dizziness, myalgia, chills, and a small increase in absolute lymphocyte count. Localized toxicities reported are erythema, edema, ulceration, weeping, scabbing, flaking, pruritis, and numbness/tingling. Other infrequent toxicities reported that may be related are abnormal LFT, abdominal cramping, nausea, vomiting, diarrhea, backache, neck pain, rhinitis, and urticaria.

**All adverse events will be recorded according to this table:**

Attribution	Grade 1	Grade 2	Grade 3	Grade 4	Grade 5
Unrelated			X	X	X
Unlikely			X	X	X
Possible	X	X	X	X	X
Probable	X	X	X	X	X
Definitive	X	X	X	X	X

Exceptions to this rule will include events and laboratory abnormalities that represent common symptoms and abnormalities of melanoma and chemotherapy and/or have no clinical significance:

- Abnormalities in hematologic parameters due to myelosuppressive therapeutic effect:
  - i. Anemia, neutropenia, lymphopenia, thrombocytopenia
  - ii. Epistaxis or bleeding except for catastrophic CNS or pulmonary hemorrhage
- Common symptoms of cancer (unless grade  $\geq 3$ ) including:
  - i. Fatigue
  - ii. Weakness
  - iii. Bone, joint or muscle pain
  - iv. Alopecia
  - v. Loss of appetite, Nausea, Vomiting
  - vi. Chemistry abnormalities (phosphorus, calcium, glucose)
  - vii. Coagulation abnormalities (shortened PT, PTT, increased fibrinogen)
- Laboratory abnormalities:
  - i. LDH (increased or decreased)
  - ii. Alkaline phosphatase (increased or decreased)
  - iii. Low levels of the following: AST, ALT, creatinine, BUN, uric acid, bilirubin, albumin, total protein
  - iv. Electrolyte abnormalities (sodium, potassium, bicarbonate, CO2, magnesium)

Abnormal laboratory test results will be captured if intervention is required.

Based on the CTCAE v.4, any grade 3 or greater toxicity will result in a dose reduction of the application of R848 from twice a week to once a week, however we will still report this AE. In addition, if this is required in 3 patients, we will temporarily halt accrual so that we can reassess the study as indicated. Abnormal lab values that are considered clinically significant by the principal investigator will be tracked. The criteria used is based on our experience with this assay in patients, was that biologically significant response is considered to be  $\geq 0.1\%$  gp100(g209-2M) tetramer + cells in the CD8 + T-cell population, and an increase of  $\geq 2$  fold of gp100(g209-2M) tetramer + cells at any time point over the pre-vaccine levels. This is based on the sensitivity of detection using our current tetramers and immunologic reagents.

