## **2.6 *TLR agonists can activate pDC and mDC and can induce inflammation***

### **a. R848 (Resiquimod)**

Resiquimod (also known as R-848) is a novel heterocyclic amine that acts as a dual TLR7 and TLR8 agonist and therefore is capable of activating both plasmacytoid dendritic cells (pDC), which express TLR7, and myeloid dendritic cells (mDC), which express TLR8. Resiquimod is a member of the imidazoquinoline family of IRMs, of which imiquimod has been most extensively characterized (and is in active clinical use for the treatment of actinic keratosis and basal cell cancer). Resiquimod is consistently more potent than imiquimod (50-100 fold) based on median minimum concentration required to elicit a 3-fold increase in IFN- $\alpha$ , TNF- $\alpha$ , and IL-12 production by human PBMC. Resiquimod can promote functional maturation of DC subsets as defined by enhanced expression of co-stimulatory molecules important for antigen presentation and T-cell activation.

Resiquimod is available in a gel formulation for topical use and has been used previously in clinical trials of herpetic lesions, actinic keratosis and anogenital warts. These studies revealed that topical resiquimod is well tolerated and capable of inducing inflammatory reactions consistent with activation of plasmacytoid and myeloid dendritic cells. As we have shown synergy between pDC and mDC in the induction of antigen-specific T-cell priming, we propose to utilize topical resiquimod over the vaccine site.

In a study of multiple doses of topical resiquimod applied to intact skin of the upper arm (1246-R848), with a maximum exposure of 2.5mg (1gm of 0.25% gel) 2x/week for 3 weeks, dose-related, but tolerable, systemic adverse effects consistent with systemic cytokine induction were observed. These included fever, chills, and transient neutropenia. Application site reactions including erythema, stinging, and pruritis were also observed. Dose-related increases in local cytokine production and T-cell infiltration were also reported.

[figure not shown]
Because the 0.25% dose provided the highest level of immune cell infiltration, we will plan to utilize a dose of 0.2% R848 2 times per week in our study (currently, this is the highest clinical grade formulation available), with the option of dose reducing to 1 time per week should patients not tolerate the treatment due to adverse reactions.

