- b. All events occurring during the conduct of a protocol and meeting the definition of a SAE must be reported to the IRB in accordance with the timeframes and procedures outlined in "University of Texas M.D. Anderson Cancer Center Institutional Review Board Policy on Reporting Serious Adverse Events". Unless stated otherwise in the protocol, all SAEs, expected or unexpected, must be reported to the IND office regardless of attribution.
- c. All grade 3-5 reactions to the vaccination and all unexpected SAEs will be reported in an expedited fashion.
- d. All life-threatening or fatal events, expected or unexpected, and regardless of attribution to the study drug, must have a written report submitted within 24 hours(next working day) of knowledge of the event to the Safety Project Manager in the IND office.
- e. The MDACC "Internal SAE Report Form for Prompt Reporting" will be used for reporting to the-IND office
- f. Serious adverse events will be captured from the time the patient signs consent until 30 days after the last application of R848. Serious adverse events must be followed until clinical recovery is complete and laboratory tests have returned to baseline, progression of the event has stabilized, or there has been acceptable resolution of the event.
- g. Additionally, any serious adverse events that occur after the 30 day time period that are related to the study treatment must be reported to the IND office. This may include the development of a secondary malignancy.
- h. The adverse events will be recorded in PDMS according to the following guidelines.

8.3.1 Reporting to FDA - Serious adverse events will be forwarded to FDA by the IND Sponsor (Safety Project Manager in the IND office) according to 21 CFR 312.32.

8.4 It is the responsibility of the PI and the research team to ensure serious adverse events are reported according to the Code of Federal Regulations, Good Clinical Practices, the protocol guidelines, and Institutional Review Board policy.

Recommended Adverse Event Recording Guidelines					
Attribution	Grade 1	Grade 2	Grade 3	Grade 4	Grade 5
Unrelated	Phase I	Phase I	Phase I Phase II	Phase I Phase II Phase III	Phase I Phase II Phase III
Unlikely	Phase I	Phase I	Phase I Phase II	Phase I Phase II Phase III	Phase I Phase II Phase III
Possible	Phase I Phase II	Phase I Phase II Phase III			
Probable	Phase I Phase II	Phase I Phase II Phase III			
Definitive	Phase I Phase II	Phase I Phase II Phase III			

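### The adverse-event exceptions in Section 8.0 are worded for chemotherapy: they can drop several low-grade R848 effects, leave the recording of neutropenia unclear, and conflict with the trial's other recording rules

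*Combined protocol and SAP*

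**What the plan says.** **Recording table, Section 8.0.** Events rated possible, probable or definitive are recorded at grades 1-5. Events rated unrelated or unlikely are recorded at grades 3-5 only.

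**Exceptions, directly below the table.** "Exceptions to this rule will include events and laboratory abnormalities that represent common symptoms and abnormalities of melanoma and chemotherapy", or that are clinically unimportant. Three groups follow:

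- "Abnormalities in hematologic parameters due to myelosuppressive therapeutic effect": low blood counts, neutropenia among them, and non-catastrophic bleeding. No grade limit is given.
- Common cancer symptoms, excepted unless grade 3 or higher. Fatigue, muscle pain, nausea and vomiting are on this list.
- Selected laboratory changes, including alkaline phosphatase in either direction and AST, ALT and bilirubin when low.

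**Safeguards in the same section.** Laboratory results that need intervention are captured, and values that the principal investigator considers clinically significant are tracked. Grade 3 or greater toxicity that leads to an R848 reduction is still reported. Section 8.0 also has two three-patient rules: one stops entry after three patients with grade 3 or greater toxicity, and the other halts accrual if three patients need the reduction.

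**What R848 is said to cause.** Section 8.0: "The most frequent systemic toxicities associated with Resiquimod are fever, fatigue, headache, pain, dizziness, myalgia, chills, and a small increase in absolute lymphocyte count". It continues: "Localized toxicities reported are erythema, edema, ulceration, weeping, scabbing, flaking, pruritis, and numbness/tingling". Nine infrequent effects that may be related come next, including nausea and vomiting. On the earlier topical study, Section 2.6 says: "These included fever, chills, and transient neutropenia".

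**Other recording rules.** Section 8.2 item h: "The adverse events will be recorded in PDMS according to the following guidelines". The table it points to, printed after Section 8.4, includes Phase II for grade 1-2 events rated possible or higher and has no exceptions. Section 7.1 sends toxicities to a toxicity sheet, also without exceptions, and schedules a CBC with differential about every 2-4 weeks.

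**The concern.** The exceptions read like text from a cytotoxic protocol. Section 6.0 gives only peptide vaccines with or without R848, so there is no chemotherapy background to filter out. In the adjuvant cohort there is no evident disease to which symptoms could be ascribed. Several excepted terms are instead effects that the protocol itself attributes to R848.

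Two things are at stake. The first is the low-grade tolerability record for a topical adjuvant, which Part 1 is well placed to describe because Arms A and B differ there only by R848. Events that are never recorded may not be recoverable. The second is consistency: the grade 3 reporting and three-patient rules presuppose that grade 3 events are captured, yet the hematology exception has no grade limit. The DSMB reviews the data annually (Section 12.0), and what it sees depends on which recording rule staff followed.

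**Working it through.** The plan states no figure on this point, so there is none to reproduce. The check compares the passages and counts terms.

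**1. Which events can the symptom exception remove?** The base table records grade 1-2 events only if rated possible, probable or definitive, and the symptom exception stops at grade 3. The two overlap only at grades 1-2 with at least possible attribution. Every record this exception can remove is therefore one that the table would have kept as at least possibly related.

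**2. How many named R848 effects are covered?** Each toxicity named in Section 8.0 was matched to the exceptions.

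| Group | Named | Clearly excepted | Arguable | Untouched |
|---|---|---|---|---|
| Frequent systemic | 8 | 2 (fatigue, myalgia) | 1 (pain) | 5 |
| Local | 8 | 0 | 0 | 8 |
| Infrequent | 9 | 2 (nausea, vomiting) | 3 (backache, neck pain, abnormal LFT via alkaline phosphatase) | 4 |
| Total | 25 | 4 | 4 | 17 |

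- Clearly excepted: 4/25 = 16%.
- Clear plus arguable: 8/25 = 32%.
- Untouched: 17/25 = 68%. These include fever, chills, headache, dizziness and all eight local reactions.

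The four clear terms are excepted at grades 1-2 only. Neutropenia comes from Section 2.6 and is additional to the 25.

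**3. Neutropenia, two readings.** If the condition about myelosuppressive effect is taken literally, no cytotoxic drug is given and the exception has little or nothing to act on. If staff apply it by term, it takes out neutropenia, a named R848 effect, at any grade. A transient fall in count could then fail both laboratory safeguards, because one needs an intervention and the other a judgement of clinical significance. The sentence that keeps grade 3 events reported is framed around a reduction from twice to once weekly, whereas Sections 3.4 and 11.0 describe weekly gel at the vaccine site. Whether it reaches Part 1 is unclear, and these passages must be reconciled.

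**4. The recording rules side by side.**

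| Place | Grade 1-2, at least possibly related | Exceptions |
|---|---|---|
| Section 8.0 | recorded | yes |
| Section 8.2 item h and its table | recorded | none |
| Section 7.1 toxicity sheet | toxicities recorded, no grade rule | none |

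The two grade-by-attribution tables agree for a Phase II trial; the exceptions are what differs. No passage says which rule governs.

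**5. Disease-free share.** Section 11.0 randomises 48 patients and its Part 2 sample-size argument assumes 24 in the metastatic cohort: 48 - 24 = 24, and 24/48 = 50%.

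**6. Can effects that stay recorded still show a difference?** The documents give no event rates, so these are assumptions. With 24 per arm and a one-sided 5% Fisher exact test, power is 0.89 for 40% versus 5%, 0.71 for 40% versus 10%, and 0.33 for 40% versus 20%. A large difference in fever, chills or local reactions would probably be seen. A moderate one is limited by sample size, not by the exceptions.

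**The case against.** The strongest reply is that little is shown to be lost. Most named toxicities are untouched, grade 3 or greater symptoms are kept, there are two laboratory safeguards, and safety is neither an objective in Section 1.0 nor a planned arm comparison in Section 11.0. The exceptions are also tied to cause, so an event judged probably due to R848 need not be read as a cancer symptom. If Section 8.2 governs, nothing is dropped. Nausea and vomiting are listed only as infrequent and possibly related.

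Much of this stands, and it rules out some stronger inferences:

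- That the record could not show an R848 safety signal, or would show equal tolerability. The 17 untouched effects contradict this.
- That laboratory changes are kept only when they need intervention. Values judged clinically significant are also tracked.
- That grade 3-4 neutropenia is lost. This is possible under one reading, but the documents do not establish it.
- That bleeding after a biopsy or leukapheresis is dropped. Bleeding sits under the myelosuppression heading, which procedural bleeding does not fit.
- That a planned adverse-event test is invalidated. None is planned.

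The argument from cause does not rescue the text. Grade 1-2 events ascribed to cancer and rated unrelated or unlikely are already outside the table. Read by cause, the symptom exception has almost nothing left to do beyond doubtful cases rated possible; read by term, it removes related events. Nor does the existence of a second rule without exceptions cure the first.

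**Conclusion.** The point holds as a recording-rule defect of limited reach. Applied as written, Section 8.0 can drop grade 1-2 fatigue, myalgia, nausea and vomiting even when rated related to study treatment: 4 of the 25 R848 toxicities it names, or up to 8 if the arguable terms are counted. It leaves open whether neutropenia is recorded at any grade, which sits badly with the grade 3 reporting and three-patient rules in the same section. It also conflicts with Sections 7.1 and 8.2.

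The consequence is under-recording of several low-grade effects. The primary T-cell endpoint is unaffected. How many events would be lost cannot be estimated, because the documents give no rates and do not say which rule governs. The conclusion assumes that staff apply the exceptions by listed term; the count assumes that myalgia and muscle pain are the same event.

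**What to change.** 1. In Section 8.0, limit the exceptions to events rated unrelated or unlikely. For the symptom list this amounts to deletion, since grade 1-2 events so rated are not recorded anyway.
2. Delete the hematology exception, or give it an explicit grade limit and remove the reference to myelosuppressive therapy.
3. Record CTCAE-graded neutropenia from the CBCs already drawn under Section 7.1, whether or not intervention is needed.
4. Reconcile Sections 7.1, 8.0 and 8.2 so that one grade-by-attribution table governs and every event rated possible or higher is recorded. State that the events counted by the grade 3 and three-patient rules come from that same record.

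The cost is amended wording and more low-grade adverse-event entries. No new visit or test is needed, because toxicity is already assessed at each visit. One limit remains: grade 1-2 recording still depends on attribution, and no blinding is described, so any descriptive table by arm should carry that caveat.
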